6.1.1 Demographics and other baseline characteristics

Demographics and other baseline characteristics will be presented by means of descriptive statistics (by group and in total). Continuous variables will be presented by means of number of observations (N), minimum (min), median, maximum (max), mean, and standard deviation (SD). Discrete variables will be presented by frequency and percentage. Difference in patient demographics between the treatment groups will be assessed using the Chi Square test to assess the similarity in treatment groups, ensuring that the outcomes are not influenced by difference in treatment group demographics.

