3.4 Method of assigning subjects to treatment groups

Subject numbers (subject ID) will be consecutively allocated in series at day of inclusion (Visit 1). Subjects will receive numbers starting at 101. Enrollment will continue until 80 subjects have been allocated a subject ID. If a subject discontinues, the subject number will not be reused.

Subjects will be randomized strictly sequentially at day of extraction and ridge preservation (Visit 2). At Visit 2 all study sites in all subjects are considered equivalent. The randomization schedule will be generated using a validated system under the responsibility of the investigatory team. 80 pieces of folded paper will contain the allocated treatment group (20 each of group A, B, C and D) and contained in an enclosed container. One piece of paper will be blindly selected by the PI or co-investigators, and the treatment group will be revealed to the clinician only following extraction of the tooth.

The randomization code papers will be stored in an enclosed and concealed container and stored by PI and co-investigators.

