6 STATISTICAL METHODS AND DETERMINATION OF SAMPLE SIZE

6.1 Statistical evaluation – general aspects

A comprehensive Statistical Analysis Plan (SAP) may be prepared before database lock. If prepared, the SAP will be kept as an appendix to the Data Management Plan. When using the terminology descriptive statistics it means that number of patients, mean, median, standard deviation, minimum and maximum values will be presented for continuous data and frequencies and percentages for categorical data.

Descriptive statistics will be given for each variable in the study and p-values may be complemented by confidence intervals as appropriate. A p-value less than 0.05 will be considered “statistically significant”.

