6.1.2 Covariates and prognostic variables

No covariates are judged to influence the outcome of the primary or any of the secondary variables, however these will be assessed using the Chi Square test.

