6.3 Determination of sample size

A sample size of 20 participants per treatment group was selected following power calculations and allowing for 10% patient dropout (has dropout rate been factored into our sample size of 20 patients per group). A sample size of 18 patients was calculated for the primary outcome variable (horizontal bone changes) with the assumption that the detectable difference would amount to 0.5mm³ with a standard deviation of 0.5. The type I error probability was set at 0.05 and the statistical power was set at 80%.

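### Sections 6.1.1 and 6.1.2 use a baseline chi-square test as assurance or check that demographics and covariates do not influence the outcome, which such a test cannot show

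*Combined protocol and SAP*

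**What the plan says.** Section 6.1.1 plans descriptive statistics for demographics and baseline characteristics, by group and in total. It then adds a test: "Difference in patient demographics between the treatment groups will be assessed using the Chi Square test to assess the similarity in treatment groups". The same sentence closes with what the test is meant to achieve: "ensuring that the outcomes are not influenced by difference in treatment group demographics".

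Section 6.1.2 is worded differently. It begins with a judgement, "No covariates are judged to influence the outcome of the primary or any of the secondary variables", and adds "however these will be assessed using the Chi Square test". It does not say what is to be cross-tabulated with what.

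The surrounding plan is as follows.
- The significance threshold is in section 6.1: "A p-value less than 0.05 will be considered" significant.
- Section 3.4 allocates by drawing papers, 20 for each of four groups.
- The outcomes are compared by unadjusted Wilcoxon rank sum tests (Synopsis, 6.2.1, 6.2.2).
- No adjusted analysis appears anywhere, and section 6.1.4 rules out subgroup analyses.
- The text of sections 3.1.2 and 3.4 names no stratification factor, and 3.4 treats all sites as equivalent. The figure on randomisation and stratification is not shown in the copy reviewed.
- Section 6.1 makes a separate SAP optional.

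**The concern.** There are three separate difficulties.

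1. A test between randomised groups asks whether chance could have produced the imbalance seen. If the randomisation was sound, the answer is known beforehand. A p-value above 0.05 does not show that the groups are alike, least of all with 20 per group.
2. Whether a covariate influences the outcome is a question about covariate and outcome. On the likely reading of 6.1.2, the chi-square crosses covariate with treatment group, so the outcome is not in the table. No sample size would make that test answer the question.
3. Section 4.1 records date of birth and body mass index. Age and BMI are continuous, and a chi-square test needs categories for them. None are given.

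What is at stake is the statement the report would be entitled to make. On the wording of 6.1.1, a set of non-significant p-values would support a claim that outcomes were free of demographic influence. A significant one could cast doubt on a sound randomisation. Neither conclusion would be justified. The chi-square is also the only step in the plan directed at prognostic imbalance. Eligible teeth run from incisors to premolars (3.2.2), and smokers of up to 10 cigarettes a day are admitted (3.2.3, 3.2.4).

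**Working it through.** **Inputs from the protocol.** Four groups of 20 (3.4, 6.3); significance at p < 0.05 (6.1); design difference 0.5 with SD 0.5 (6.3). The documents give no operating figure for the chi-square test, no factor prevalence and no covariate effect, so those below are illustrations or assumptions.

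**Step 1. The stated group size.** Section 6.3 says "A sample size of 18 patients was calculated for the primary outcome variable".
- Normal approximation: n = 2 × (1.96 + 0.84)² × (0.5/0.5)² = 15.7, so 16 per group.
- Exact t-test: 17.
- Allowing for Wilcoxon efficiency: 17/0.955 = 17.8, so 18.
- Dropout: 18/0.9 = 20.

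The group size is therefore reproduced, and 20 per group is the right basis for what follows.

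**Step 2. Two-group chi-square on a 30-point gap.** With a of 20 in one group and c of 20 in the other, b = 20 − a and d = 20 − c, the uncorrected statistic is 40(ad − bc)² / [20 × 20 × (a + c)(b + d)].
- 6/20 v 12/20: ad − bc = 6×8 − 14×12 = −120. The statistic is 40 × 14,400 / (400 × 18 × 22) = 3.64, p = 0.057. With continuity correction, 40 × (120 − 20)² / 158,400 = 2.53, p = 0.112. Not flagged either way.
- 4/20 v 10/20: ad − bc = 4×10 − 16×10 = −120. The statistic is 40 × 14,400 / (400 × 14 × 26) = 3.96, p = 0.047. Flagged uncorrected; with correction p = 0.097, not flagged.
- Over the whole range, the uncorrected test passes 30-point gaps from 25% v 55% to 45% v 75% (p = 0.053 to 0.058) and flags those nearer the extremes. With correction it passes them from 10% v 40% to 60% v 90% (p = 0.068 to 0.114).

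**Step 3. Four-group chi-square (3 df).** Counts 6, 7, 6, 12 of 20: total 31 of 80, proportion 0.3875, mean count 7.75. The squared deviations sum to 3.0625 + 0.5625 + 3.0625 + 18.0625 = 24.75. The statistic is 24.75 / (20 × 0.3875 × 0.6125) = 5.21, p = 0.16. Not flagged.

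**Step 4. How often such a gap arises by chance.** Simulation of one binary factor with an assumed prevalence of 50% in four groups of 20:
- some two groups differ by at least 30 points in 30% of trials, and the four-group test passes 84% of those;
- one given pair differs by at least 30 points in about 8% of trials.

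**Step 5. Chance alarms.** With k independent baseline tests at 0.05, the chance of at least one p < 0.05 is 1 − 0.95^k. For k = 5 this is 0.23; for k = 10 it is 0.40. Section 4.1 lists more than ten items. Some are plausibly correlated, so independence is an assumption.

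**Step 6. What an unflagged gap could do.** Shift in the contrast = imbalance × effect of the factor. For an assumed effect of 0.5 to 1.0 SD:
- 0.30 × 0.5 = 0.15 SD and 0.30 × 1.0 = 0.30 SD;
- the design difference is 0.5/0.5 = 1 SD, so the shift is 15% to 30% of it;
- with standard error √(2/20) = 0.316 SD, the two-sided error in a trial that has this imbalance is about 8% to 16% (normal approximation).

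These figures are conditional on the imbalance having occurred.

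**The case against.** The strongest reply is that little depends on these two sentences. The Wilcoxon comparisons run whatever the chi-square shows. Section 6.1.1 already requires by-group summaries, so a reader would see an imbalance. No reporting rule turns the chi-square result into a written conclusion, and randomisation protects the error rate over all allocations. All of this stands, and it limits the harm. It does not rescue the purpose that 6.1.1 itself gives for the test.

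Four stronger readings are tempting, and the documents do not support them.

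- A reader might infer that both sections treat the chi-square as a guarantee. Only 6.1.1 does, and only for demographics. Section 6.1.2 rests on a judgement and adds the test as a check, and its wording leaves the cross-tabulation open.
- A reader might infer that the test passes any 30-point imbalance. Step 2 shows that it does not. The protocol also does not say whether the test is pairwise or four-group, or whether it is corrected.
- A reader might quote the power of the test to detect a true 30-point difference between groups. Under sound randomisation no such difference exists, so power is not the relevant measure.
- A reader might conclude that the primary comparison is biased. The shift in Step 6 applies to a trial in which the imbalance happened to fall that way. Averaged over randomisations it is zero.

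**Conclusion.** The concern holds as a fault in the stated inference. It is not a fault in the primary test. Followed as written, section 6.1.1 would draw reassurance from a test that cannot give it. The check in 6.1.2, on its likely reading, does not address influence on the outcome. The chi-square can miss mid-range gaps of 30 points at 20 per group, and it raises at least one chance alarm in 23% to 40% of trials if 5 to 10 independent variables are tested.

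The conditional shift of 0.15 to 0.30 SD rests on an assumed factor effect of 0.5 to 1 SD, for which the documents give no value. Overall type I error is intact and no primary p-value depends on the chi-square. The harm is an unsupported statement about influence, and a plan with no adjusted analysis to fall back on. It should be corrected, because the correction is cheap and uses data that are for the most part already collected.

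**What to change.** **Section 6.1.1.** Delete the chi-square sentence together with its closing assurance clause. Keep the descriptive table, by group and in total, without p-values.

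**Section 6.1.2.** Replace the chi-square with one pre-specified sensitivity analysis of the primary comparisons (A v B, A v C, A v D), run whatever the baseline table shows and adjusted for a few recorded factors. Two workable forms are:
- a rank-based ANCOVA;
- a van Elteren test stratified by one factor at a time, for example tooth class with its categories defined in advance, or smoking.

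Describe the result as an adjusted treatment comparison. Neither form is a test of whether the covariate affects the outcome, and the text should not present it as one.

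**Cost.** Two changes of wording and one extra analysis, with no new patients or procedures. Tobacco use is already recorded (4.1). The study tooth is known from eligibility (3.2.2), but the CRF should be checked to confirm that it is captured. At 20 per arm some strata may be sparse, and a stratum with only one arm contributes nothing. That is the reason for stratifying by one factor at a time.

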6.1.2 Covariates and prognostic variables

No covariates are judged to influence the outcome of the primary or any of the secondary variables, however these will be assessed using the Chi Square test.

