A circumferential sulcular incision will be placed around the teeth to be extracted. Periotomes and luxators will be used to extract the tooth with minimal trauma to the adjacent tissues. The socket wall will be examined for any dehiscence greater than 3mm or fenestrations. If these are present, the patient will be excluded from the study. Gauze will be placed in the area to produce wound hemostasis

Immediately following tooth extraction, the patient will have a small field-of-view cone beam computed tomography (CBCT) image produced whilst wearing the radiographic stent. Images will provide pre-preservation data for horizontal and vertical bone locations.

Following CBCT imaging, a ridge preservation procedure will be completed as follows:

- Group A: Symbios demineralized cortical-cancellous granule mix reconstituted in sterile saline will be used to augment the socket and will be covered by a Symbios OsteoShield Collagen resorbable membrane.
- Group B: Symbios OsteoGraf LD-300 reconstituted in sterile saline will be used to augment the socket and will be covered by a Symbios OsteoShield Collagen resorbable membrane.
- Group C: Symbios OsteoGraf/N-300 reconstituted in sterile saline will be used to augment the socket and will be covered by a Symbios OsteoShield Collagen resorbable membrane
- Group D: Socket covered with Symbios OsteoShield Collagen resorbable membrane and no grafting material, allowing socket to heal.

Grafted sockets will be closed with a barrier membrane using 5-0 chromic gut suture. It is anticipated that a cross mattress and/or simple loop sutures will be employed.

All surgical procedures listed above are standard clinical procedures, including preparation and utilization of grafting materials list above.

Post-Surgical Procedures

Buccal and crestal photographs of the surgical site will be obtained, which is standard clinical practice in the School of Dentistry.

Standard UNC post-operative instructions will be given which includes the use of a Chlorhexidine rinse 2 times daily for 2 weeks.

This visit includes a CBCT for research purposes only. The remainder of treatment is standard clinical protocol.

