3.2.2 Inclusion criteria

For inclusion in the study subjects must fulfill all of the following criteria:

1. Provision of informed consent
2. ≥ 18 years and ≤ 75 years
3. Good physical health (ASAI/II)
4. Extraction of maxillary premolar, canine or incisor, or mandibular premolar and canine required (4-13, 20-22, 27-29)
5. Teeth adjacent (mesial and distal) to study site must consist of two stable natural teeth with minimal restorations, without signs of periodontal bone loss (> 3 mm) and/or significant soft tissue deficiencies

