4.2.1.1.1 Methods of assessment

CBCT images will be obtained at baseline (Visit 2) and 3 months following alveolar ridge augmentation (Visit 4). Using 3D imaging software, the bone will be segmented to produce an STL file. Following this, the segmented images will be superimposed and aligned through a fiducial point registration algorithm, and at the same time, the same region of interest will be cropped in each scan and exported as a separate model. The volume of the baseline and 3 month scan will be calculated and compared.

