4.2.1.1.2 Derivation or calculation of variable

The changes in the bone volume between baseline (Visit 2) and 3 months (Visit 4) will be measured electronically using 3D analysis software. The change for each study site will be compared longitudinally and the average for each treatment group will be calculated and compared among treatment and control groups.

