6.2 Method of statistical analysis

6.2.1 Primary objective

The primary objective is to compare dimensional bone changes from baseline (Visit 2) to three months (Visit 4) occurring in a single bound extraction site following ridge preservation using three different grafting materials and membrane, and one no graft membrane only group.

Assume the change is denoted C_A , C_B , C_C , and C_D , for group A, B, C, and D respectively. The null-hypothesis is then to test if:

$H_0: C_A = C_i$ ($i = B, C$, and D respectively)
can be rejected and hence
 $H_1: C_A \neq C_i$ ($i = B, C$, and D respectively)
accepted.

H_0 will be tested by means of the Wilcoxon rank sum test. A p-value less than 0.05 will be regarded statistically significant.

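### Bone-volume change is compared without adjusting for baseline volume, which is measured before grafting at every site

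*Combined protocol and SAP*

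**What the plan says.** Section 6.1.2 says "No covariates are judged to influence the outcome of the primary or any of the secondary variables" and adds only that covariates will be looked at with a Chi-square test. Section 6.1.1 applies Chi-square tests to demographics, described as "ensuring that the outcomes are not influenced by difference in treatment group demographics". For the primary objective (6.2.1), group A is compared with B, C and D on change from Visit 2 to Visit 4: "H_0 will be tested by means of the Wilcoxon rank sum test". No section offers an adjusted analysis, and section 6.1 leaves a separate SAP optional.

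Baseline volume is nevertheless collected. Section 3.1.2 places the scan right after extraction and the graft after the scan ("Following CBCT imaging, a ridge preservation procedure will be completed as follows"). Section 4.2.1.1.1 says "The volume of the baseline and 3 month scan will be calculated and compared". Section 4.2.1.1.2 defines the outcome as follows: "The changes in the bone volume between baseline (Visit 2) and 3 months (Visit 4) will be measured electronically". It does not say whether change is absolute or a percentage of baseline.

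Section 3.4 says "At Visit 2 all study sites in all subjects are considered equivalent", although inclusion criterion 4 (3.2.2) admits maxillary incisors and both canines and premolars in either jaw.

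**The concern.** Baseline volume precedes grafting in every arm, so it is a legitimate covariate and is already in hand. Sites of different tooth type and jaw can be expected to differ in size, and the outcome is change from that same baseline, so a link between the two is plausible. Section 6.1.2 gives no reason for ruling it out.

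The text describes one container of 80 papers and names no stratification factor, so nothing visible controls imbalance in site size by design. The Chi-square checks do not control it either. A balance test adjusts nothing, it does not suit a continuous volume unless the volume is categorised, and the plan does not say what follows if an imbalance is found.

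At stake are power, and the credibility of the result in the particular trial that is drawn. If baseline is related to change and the arms happen to differ at baseline, part of any observed difference is due to that imbalance.

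**Working it through.** **Inputs.** From 6.3: difference 0.5, SD 0.5, type I error 0.05, power 80%, 18 evaluable per group, 10% dropout. From 3.4: 20 per group. The alternative in 6.2.1 is two-sided. Section 6.3 attaches these figures to horizontal bone change; here the standardized effect 0.5/0.5 = 1.0 SD is assumed to carry over to volume. R² is the within-arm share of variance in change explained by baseline volume. The documents do not give it, so 0, 0.10, 0.25 and 0.50 are assumptions.

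**The plan's own figure.** n = 2(1.960 + 0.842)² × (0.5/0.5)² = 15.7. The exact t-test needs 16.7. Dividing by the Wilcoxon relative efficiency 3/π = 0.955 gives 17.5, so 18 per group, and 18/0.9 = 20. The stated size reproduces.

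**How often imbalance occurs.** In baseline SD units, the difference in means between two arms of 18 has SD √(2/18) = 0.333. So P(|difference| ≥ 0.5) = P(|Z| ≥ 1.5) = 0.134 per pair, and 0.305 for at least one of A-B, A-C and A-D.

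**What it does.** A 0.5 SD imbalance shifts the unadjusted difference by 0.5 × √R² = 0.16, 0.25 and 0.35 SD at R² 0.10, 0.25 and 0.50.

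**Simulation.** Change = √R² × baseline + √(1 − R²) × error + effect; 18 per arm; two-sided 5%; 20,000 runs per power cell and about 26,500 imbalanced trials per R². The adjusted test is Quade's rank analysis of covariance done per pair: rank change and baseline over the two arms, regress one set of ranks on the other, and compare the residuals by arm. Normal errors, A against D:

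| R² | 0 | 0.10 | 0.25 | 0.50 |
|---|---|---|---|---|
| Power at 1.0 SD, Wilcoxon (%) | 80.5 | 79.6 | 80.6 | 80.3 |
| Power at 1.0 SD, adjusted (%) | 80.2 | 82.9 | 88.9 | 96.5 |
| False positives given imbalance ≥ 0.5 SD, Wilcoxon (%) | – | 7.4 | 11.9 | 19.1 |
| False positives given imbalance ≥ 0.5 SD, adjusted (%) | – | 4.2 | 4.3 | 4.4 |

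A second simulation (40,000 trials per setting, correlations 0.3, 0.5 and 0.7) agrees: 7.6%, 11.7% and 19.6% unadjusted against 4.1–4.5% adjusted. With a true 1 SD effect and an adverse imbalance of at least 0.5 SD, unadjusted power was 62%, 45% and 30%, against 76%, 81% and 92% adjusted. The overall level was about 5% for both tests.

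**Other error shapes.** With exponential errors in either direction and t errors on 3 df, the adjusted rank test was above Wilcoxon at every R² of 0.10 or more. At 18 per arm it was never more than 0.7 points below it. Normal-theory ANCOVA was about 5 to 10 points below Wilcoxon with these errors at R² of 0.10 or less, which is why a rank-based form is preferred.

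**Scale of change.** Suppose percent loss is independent of baseline (assumed baseline CV 20–40%; arms A-C and D at mean losses of 1 and 2 SD, or 2 and 3 SD). On percent change, computed for the first pair of means, both tests have about 80% power. On absolute change, Wilcoxon has 54–76% and the adjusted test 76–79%.

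**The case against.** The strongest case is that the planned test is valid and this is optimisation. Its overall level is about 4.7%, and analysing change already subtracts baseline. That is right as to validity. But subtracting baseline does not remove a dependence of change on baseline, as the absolute-change runs show.

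The benefit also rests on an R² that the documents do not give, and there is no gain at R² = 0 or on percent change under proportional loss. This stands, and it is why the result is a range and why the scale must be defined first.

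The conditional error rates describe only the imbalanced trials. In the other 87%, Wilcoxon ran below nominal, at 4.2%, 3.9% and 2.4%. True: the issue is how the error is spread over draws, not its average.

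The main runs assume the same slope in each arm, whereas A-C are filled and D is not. With slope 0.5 in A and 0 in D, power was 79.7% against 81.6%, and false positives given imbalance were 6.8%. With slopes +0.5 and −0.5 it was 80.0% against 79.8%. So the gain can shrink to nothing, but the loss stays below 1 point.

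The cost at R² = 0 is slightly larger at 20 per arm (84.8% against 83.9%; about 1 point in another run). Within imbalanced trials at R² = 0 and 18 per arm it is about 5 points (81.6% against 76.4%). The cost is therefore small on average, not in every draw.

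Finally, section 3.1.2 has a heading that mentions stratification, and Figure 2 is not shown. A stratified draw would reduce imbalance, but the text names no factor, and the planned analysis would still be unadjusted.

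**Conclusion.** The concern holds. The planned comparison is valid on average but gives up precision, and protection against chance imbalance, that a baseline value already collected could supply. An imbalance of at least 0.5 SD is expected in about 13% of trials for a given pair and about 30% for at least one of the three planned pairs. The false-positive rate in such trials is then 7–19% unadjusted against about 4% adjusted, for assumed R² of 0.10 to 0.50. Power rises from about 80% to 83–97% over the same range. The average price if baseline is unrelated to change is about 1 point at most.

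The size depends on R², on similar slopes across arms, on the 1.0 SD effect carrying over to volume, and on the scale chosen for change. It is a weakness that should be corrected, not a flaw that invalidates the trial.

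**What to change.** 1. In 4.2.1.1.2 and 6.2.1, state whether change is absolute or percent of baseline.
2. Make the primary analysis a Quade-type rank analysis of covariance with baseline volume as the only covariate, done separately for A-B, A-C and A-D with ranks taken over the two arms compared. A single four-arm fit with pooled error gains about 1 point of power under normal errors. However, its A-B test ran at 4.0–7.5% when only D differed, which is the situation section 2.1 expects. If a four-arm fit is used, each contrast should take its error from the two arms compared.
3. Keep the unadjusted Wilcoxon test as a sensitivity analysis. Add a normal-theory ANCOVA for estimates and confidence intervals, noting that it may disagree with the rank p-value. Jaw may enter a sensitivity analysis only.
4. Treat the CBCT linear bone outcomes in the same way, each with its own baseline. For soft tissue, first reconcile the baseline visit: 4.2.2.2.2 names Visit 2, while 3.1.1 and Table 1 take the baseline impression at Visit 1.
5. Rewrite 6.1.2 to match, and present baseline tables descriptively in place of the Chi-square tests in 6.1.1.

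The cost is wording and one covariate degree of freedom, with no extra patients, visits or scans. Timing matters: the protocol is dated October 2016 and estimates the last subject's completion in Q3 2016. The change counts as prespecified only if it is made before outcomes are compared by arm, in 6.2.1 or in the SAP that section 6.1 allows before database lock. If that point has passed, report the adjusted analysis as a post hoc sensitivity analysis.
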